## 2. Study Objectives

To evaluate the safety and efficacy of topical ophthalmic 0.003% AR-15512 compared to its vehicle administered twice daily (BID) in subjects with dry eye disease (DED).

### 2.1 Study Endpoints

[REDACTED] efficacy endpoints in [Section 2.1.1](#), [Section 2.1.2](#), and [Section 2.1.3](#) will be reported for study eye only unless otherwise specified in [Section 13.4](#), [Section 13.5](#), and [Section 13.6](#) respectively. The “Baseline” in [Section 2.1.1](#), [Section 2.1.2](#), and [Section 2.1.3](#) refers to Baseline (Day 1) visit unless otherwise specified.

#### 2.1.1 PRIMARY ENDPOINT

- Proportion of subjects with  $\geq 10$  mm increase (post-drop on Day 14 vs pre-drop at Baseline) in unanesthetized Schirmer score on Day 14

#### 2.1.2 SECONDARY ENDPOINTS

- Change from baseline in global symptom assessment in dry eye (SANDE) score on Day 28
- Change from baseline (post-drop on Day 14 vs pre-drop at Baseline) in unanesthetized Schirmer score on Day 14
- Proportion of subjects with  $\geq 10$  mm increase (post-drop on Day 1 vs pre-drop at Baseline) in unanesthetized Schirmer score on Day 1

- Change from Baseline (post-drop on Day 1 vs pre-drop at Baseline) in unanesthetized Schirmer score on Day 1
- Proportion of subjects with  $\geq 10$  mm increase (post-drop on Day 90 vs pre-drop at Baseline) in unanesthetized Schirmer score on Day 90
- Change from baseline (post-drop on Day 90 vs pre-drop at Baseline) in unanesthetized Schirmer score on Day 90
- Change from baseline in global SANDE score on Day 90
- Change from baseline in SANDE frequency score on Day 90
- Change from baseline in SANDE severity score on Day 90
- Change from baseline in eye dryness score (EDS) – VAS on Day 90
- Change from baseline in ocular discomfort score (ODS) – visual analog scale (VAS) on Day 90

#### **2.1.4 SAFETY VARIABLES**

The safety variables include the following:

- Adverse events (AEs)

- Hematology, chemistry, and urinalysis
- Vital signs (heart rate and blood pressure)
- Corrected visual acuity
- Slit-lamp biomicroscopy
- Intraocular pressure (IOP)
- Dilated fundus exam

## 2.2 Statistical Hypotheses

The primary endpoint will be tested as follows:

$H_{01}$ : The difference between study eyes treated with AR-15512 (0.003%) and study eyes treated with vehicle, in the proportion of subjects with  $\geq 10$  mm increase in unanesthetized Schirmer score on Day 14 = 0.

$H_{11}$ : The difference between study eyes treated with AR-15512 (0.003%) and study eyes treated with vehicle, in the proportion of subjects with  $\geq 10$  mm increase in unanesthetized Schirmer score on Day 14  $\neq 0$ .

## 2.3 Estimands

### 2.3.1 ESTIMAND 1 (PRIMARY ESTIMAND)

The primary comparison will be based on the ITT population targeting the treatment effect attributable to the randomly assigned treatment, regardless of compliance to study treatment and assuming subjects who discontinued due to lack of efficacy, AEs, or disallowed concurrent treatments follow the behavior of subjects in the reference arm for the duration of the study and subjects who discontinued for other reasons (outside of lack of efficacy, AEs or use of disallowed treatment) would follow the behavior of subjects who are still in the study under same randomly assigned treatment.

- Population: subjects in the ITT population with DED defined through enrollment criteria
- Endpoint:
  - Proportion of subjects with  $\geq 10$  mm increase in unanesthetized Schirmer score on Day 14
- Intercurrent event:
  - Non-optimal treatment compliance is ignored. [treatment policy strategy]
  - Withdrawal due to lack of efficacy, AEs, or disallowed concurrent treatment - multiple imputations using vehicle treatment group regardless of randomized treatment group is used to impute missing data. [hypothetical strategy, missing not at random]
  - Withdrawal due to reasons other than lack of efficacy, AEs, or disallowed concurrent treatment - multiple imputations using randomized treatment is used to impute missing data. [hypothetical strategy, missing at random]

- Population-level summary:
  - Difference in the proportion of subjects with  $\geq 10$  mm increase in unanesthetized Schirmer score on Day 14 between AR-15512 (0.003%) and vehicle

[figure not shown]

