#### 6.10.1 Actions after Discontinuation

Also see Early Termination Procedures (Section [7.3](#)).

All subjects who discontinue study intervention due to a report of an AE must be followed and provided appropriate medical care until their signs and symptoms have remitted or stabilized or until clinically meaningful abnormal laboratory findings have returned to acceptable or pre-study limits.

For subjects who choose to withdraw consent or who are discontinued for non-compliance prior to completing the study, every possible effort should be made by the Investigator to assure there is a final visit that includes all examinations listed for the Early Termination Visit.

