### **7.3 Early Termination Procedures**

Every effort should be made to perform the following procedures at the Early Termination visit.

- Collection of used and unused study intervention
- Concomitant medication review
- AE review
- Vital signs (heart rate and blood pressure)
- Urine pregnancy test (WOCBP only)
- Corrected visual acuity
- Slit-lamp biomicroscopy
- Hematology, chemistry, and urinalysis
- Intraocular Pressure
- Dilated Fundus Exam
- Study Exit

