## 12. APPENDICES

### Appendix 1 Schedule of Visits and Procedures

Visit 	Start of 2 Week Run-In (AR-15512 Vehicle)	Randomized Study Intervention Period (BID-OU, 1:1 Randomization 0.003% AR-15512: AR-15512 Vehicle)							Early Termination
		Screening (Day -14)	Baseline (Day 1)	Day 7	Day 14	Day 28	Day 60	Day 90 (Study Exit)	
Visit Window (Days)	+3 	N/A	±2	±2	±2	±5	-2/+5	N/A	
Informed consent	X								
Demographics	X								
Collection of used / unused study intervention		X		X	X	X	X	X	X
Medical, ophthalmic, and surgical history	X								
Prior or concomitant medication review	X	X	X	X	X		X	X	
AE review	X	X	X	X	X		X	X	
Vital signs (heart rate and blood pressure)	X	X					X	X	
Urine pregnancy test (WOCBP only)	X	X					X	X	
Symptom questionnaire (VAS) (Ocular Discomfort, Eye Dryness [REDACTED])	X	X	X	X	X		X		
SANDE questionnaire (VAS)	X	X	X	X	X		X		
Corrected visual acuity		X	X	X	X	X		X	X
Slit-lamp biomicroscopy		X	X	X	X	X		X	X

	Start of 2 Week Run-In (AR-15512 Vehicle)	Randomized Study Intervention Period (BID-OU, 1:1 Randomization 0.003% AR-15512: AR-15512 Vehicle)						
		Screening (Day -14)	Baseline (Day 1)	Day 7	Day 14	Day 28	Day 60 	Day 90 (Study Exit)
Visit 								
At least 10-minute rest period	X	X	X	X	X		X	
CAE exposure	X							
Inclusion and exclusion criteria	X	X						
Randomization		X						
Dispensing of study intervention 	X	X		X	X	X		
At least 30 and up to 45-minute rest period		X	X	X	X		X	
Pre-drop unanesthetized Schirmer test		X	X	X	X		X	
At least 15 and up to 20-minute rest period		X	X	X	X		X	
In office administration of study intervention 	X	X	X	X	X		X	
Post-drop unanesthetized Schirmer test		X	X	X	X		X	
Hematology, chemistry, and urinalysis		X					X	X
Intraocular pressure	X	X					X	X
Dilated fundus exam	X	X					X	X
Study exit							X	X

1. All office visits must be arranged at approximately the same time of day  $\pm$  1 hour
2. The Baseline visit should be scheduled between 11 and 14 days after the Screening visit. If absolutely necessary, the Baseline visit may be delayed up to 7 days (extending the run-in period to a maximum of 21 days)
3. Administered every 5 minutes while in the CAE
4. Day 7 Randomized Intervention Kit is not to be dispensed home to the subject. A single vial is used at the Day 7 visit and then returned to the kit. The single used vial as well as remaining 4 unused vials are to be retained for accountability.

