#### **13.2 Secondary Efficacy Assessments**

##### **13.2.1 SYMPTOM ASSESSMENT IN DRY EYE QUESTIONNAIRE**

The SANDE questionnaire is comprised of 2 unique VASs to assess the frequency and severity of DED symptoms. Subjects will be asked to complete the SANDE to rate both the frequency and severity of DED symptoms for both eyes together. Each of the two questions will be accompanied by a VAS. The assessment line length of the scale will be 100 mm and will be similar to the following depiction (Figure 3). Higher scores indicate greater frequency or severity of symptoms of dryness and/or irritation. In addition, a global SANDE score is also collected in the eCRF, which is calculated by multiplying the frequency score by the severity score and obtaining the square root rounded to the nearest whole number.

The SANDE will be administered at Screening, Baseline (Day 1), and Days 7, 14, 28, and 90. The frequency, severity and global SANDE score will be summarized.

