### 13.2.2 SYMPTOM QUESTIONNAIRE

Subjects will be asked to rate each of the following DED symptoms (OU), over the last 24 hours, each on a separate VAS: ocular discomfort (ODS), eye dryness (EDS), [REDACTED] For each VAS, subjects will be asked to place a vertical mark on the horizontal line to indicate the level of each symptom, with 0 corresponding to "No Symptom" and 100 corresponding to "Maximal Symptom". The assessment line length of the scale will be 100 mm and will be similar to the following depiction (Figure 4). The questionnaire will be administered at Screening, Baseline (Day 1), and Days 7, 14, 28, and 90. The ODS, EDS, [REDACTED] scores will be summarized separately.

[figure not shown]

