### 13.5 Secondary Efficacy Analyses

The secondary efficacy endpoints are listed in [Section 2.1.2](#). Changes from Baseline will be summarized by treatment group using continuous summary statistics and analyzed using an analysis of covariance (ANCOVA) model with terms for baseline value, treatment, and analysis center. [REDACTED]

[REDACTED] Least squares (LS) mean for each treatment group and for the difference between treatment groups will be presented from the model together with two-sided p-values and 95% CIs. [REDACTED]

[REDACTED].

Specifically, the global SANDE as well as SANDE severity and SANDE frequency scores will be analyzed:

- With methodology in Estimand 1 ([Section 2.3.1](#)) using ITT population;

All other secondary efficacy endpoint will be analyzed:

- With methodology in Estimand 1 ([Section 2.3.1](#)) using ITT population;

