#### **14.4 Corrected Visual Acuity**

The logarithm of the minimum angle of resolution (logMAR) visual acuity in both eyes will be assessed using an Early Treatment of Diabetic Retinopathy Study (ETDRS) Series 2000 chart at Screening, Baseline (Day 1), and Days 7, 14, 28, 90, or ET.

The actual and change from baseline in logMAR will be summarized for each eye (study eye and fellow eye) using continuous descriptive statistics by visit for each treatment group. The actual and changes from baseline to maximum on-treatment value (i.e. the worst on-treatment) will be summarized as well. The maximum on-treatment value is the highest logMAR value for each subject and eye from all post-baseline scheduled or unscheduled visits. In addition, change from baseline categories will be summarized using counts and percentages including the following categories: <= 0, >0 to <=0.09, >= 0.10 to <=0.19, >=0.20 to <=0.29, and >=0.30 for each eye (study eye and fellow eye) by visit and for each treatment group. A subject listing of corrected visual acuity will also be produced.

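### Does the lack of a SANDE or symptom VAS score at the Early Termination visit undermine the imputation of the Day 90 symptom endpoints?

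*SAP*

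**What the plan says.** Estimand 1 (SAP 2.3.1) ignores non-optimal compliance and splits withdrawals into two classes. Those due to lack of efficacy, adverse events or disallowed treatment are imputed from vehicle. The others follow this rule: "Withdrawal due to reasons other than lack of efficacy, AEs, or disallowed concurrent treatment - multiple imputations using randomized treatment". It is labelled a hypothetical strategy under missing at random. SAP 13.5 carries the method to the secondary endpoints ("Specifically, the global SANDE as well as SANDE severity and SANDE frequency scores will be analyzed" with Estimand 1 in the ITT population) and gives the same method for all the other secondaries.

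On data collection, Protocol 7.3 opens with "Every effort should be made to perform the following procedures at the Early Termination visit". Its list covers drug return, medication and adverse event review, vital signs, pregnancy test, acuity, slit lamp, laboratory tests, intraocular pressure, fundus exam and exit. It has no symptom score. In Protocol Appendix 1 the rows for "SANDE questionnaire (VAS") and the symptom questionnaire carry no ET mark. The SAP agrees. Section 13.2.1 states "The SANDE will be administered at Screening, Baseline (Day 1), and Days 7, 14, 28, and 90", and 13.2.2 states "The questionnaire will be administered at Screening, Baseline (Day 1), and Days 7, 14, 28, and 90". The safety sections, by contrast, do name ET; for acuity (14.4) the wording is "chart at Screening, Baseline (Day 1), and Days 7, 14, 28, 90, or ET". Day 60 is for dispensing and collection only (Protocol 6.5, Table 3).

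Protocol 6.10.1 asks sites to try for a final visit "For subjects who choose to withdraw consent or who are discontinued for non-compliance prior to completing the study". SAP 8.5 confines ET data to listings.

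**The concern.** Non-compliance is a listed reason for leaving the study, and Protocol 6.10 says that it can mean not using the study intervention. Such a subject falls in the own-arm class. An AR-15512 subject who stopped the drops is then given Day 90 symptom scores modelled on AR-15512 subjects who stayed. If symptoms fall back to vehicle level once the drops stop, the imputed scores are too good and the Day 90 comparison leans toward AR-15512.

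An exit symptom score would show whether that had happened. The protocol already asks for an ET visit in these cases, the questionnaires are short and self-completed, and the information cannot be recovered later. The last scheduled score before Day 90 is at Day 28, nominally 62 days earlier. Five of the eleven secondaries in SAP 2.1.2 are Day 90 symptom scores: global SANDE, SANDE frequency, SANDE severity, eye dryness and ocular discomfort. The omission therefore looks like a cheap safeguard left out.

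**Working it through.** **Inputs from the documents.** SANDE difference at Day 28: 7.9 (Protocol 9.2) or 8.3 (SAP 5), in favour of AR-15512. Common SD 17.72, 202 analysed per arm, 230 randomized per arm, 10% dropout.

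**Assumptions, because the documents give no figure.** The Day 28 effect and SD hold at Day 90. A non-user has vehicle-like symptoms. The slope between visits, r, lies between 0.4 and 0.7. No effect or SD is stated for eye dryness or ocular discomfort, so only SANDE is computed.

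**1. The plan's own figures.** Two-sample t, 202 per arm, two-sided 0.05: power is 0.994 for 7.9 and 0.997 for 8.3, so the stated 99% reproduces. 202 / 0.9 = 224.4, rounded up to 225 per arm or 450 in total, close to the 460 planned.

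**2. Standard error of the difference.** 17.72 × √(2/202) = 1.763 points.

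**3. Largest shift per 1% of the arm** (2.3 of 230 subjects), when no earlier score reflects the non-use:
- 0.01 × 7.9 = 0.079; 0.079 / 1.763 = 4.5% of one standard error
- 0.01 × 8.3 = 0.083; 0.083 / 1.763 = 4.7% of one standard error

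At 2% of the arm the shift is 0.158 to 0.166 points, about 9% of one standard error.

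**4. What an exit score would remove.** Suppose the ET score has already moved by the full effect d and predicts Day 90 with slope r. The imputed value then moves by r × d, and (1 − r) × d remains. Per 1% of the arm:

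| d | r | Remains: 0.01 × d × (1 − r) | Removed: 0.01 × d × r | Removed / 1.763 |
|---|---|---|---|---|
| 7.9 | 0.4 | 0.047 | 0.032 | 1.8% |
| 7.9 | 0.7 | 0.024 | 0.055 | 3.1% |
| 8.3 | 0.4 | 0.050 | 0.033 | 1.9% |
| 8.3 | 0.7 | 0.025 | 0.058 | 3.3% |

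The gain is about 0.03 to 0.06 points, or 2 to 3% of one standard error. A Day 7, 14 or 28 score that already reflects the non-use would do the same work if it enters the imputation model.

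**5. Extreme bound.** Let the whole 10% dropout be of this kind (23 of 230). The shift is 0.10 × 7.9 = 0.79 or 0.10 × 8.3 = 0.83 points, that is 0.45 to 0.47 standard errors. The effect left is 7.11 or 7.47, and power with 202 per arm is 0.980 or 0.988.

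**6. Whether collecting the score would change the analysis.** Under SAP 8.5 an ET score would reach only the listings. To affect the result it would need a defined place in the imputation. Completers have no ET score, so it would have to stand in for Day 28. The Day 28-to-Day 90 relation among completers would then be applied to scores taken at any time between those visits. That is open to dispute in itself.

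**The case for a change.** The best case for acting is that the facts are right and the cost looks low. No symptom score is planned at ET, sites are already asked to hold that visit, and missing at random is least secure for someone who left because the drops were not being used. The case does not depend on a large effect, since an untestable assumption is better informed than not. A sensitivity analysis that imputes these withdrawals from vehicle would need no new data. In addition, SAP 9 lists lack of efficacy as a reason for discontinuation and Protocol 6.10 does not, although that reason decides the imputation class.

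The facts stand, and so does the point that exit scores are informative in principle. The rest is weaker:

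- The shift in steps 3 to 5 is measured against the symptoms of subjects who are off drug. SAP 2.3.1 declares a different target: these subjects are taken to follow those still in the study on the same arm. Compliance is ignored, so those subjects include poor compliers and full use is not assumed.
- Non-compliance also covers missed visits. Subjects who leave for that reason are among the least likely to attend an ET visit.
- The SAP cites a clarification letter of 16 February 2023, nine months after the protocol revision of 13 May 2022. An amendment might reach few subjects or none.
- Protocol 9.1.3 already plans robustness analyses under missing not at random, although its wording concerns the primary analysis. Much of the SAP's missing-data and sensitivity text is redacted, so a further sensitivity analysis cannot be called absent.
- The mismatch on lack of efficacy is clerical. The protocol list is permissive and ends in an open category, and SAP 1 says that the SAP supersedes the protocol on analysis methods.

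**Conclusion.** The concern does not call for a change. The ET visit collects no symptom score for any reason for withdrawal, so imputation of Day 90 symptoms rests on Day 28 or earlier scores. That fits the declared hypothetical, missing-at-random strategy and is a fair trade-off.

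If non-users have vehicle-like symptoms and the Day 28 planning values hold at Day 90, the lean toward AR-15512 is at most about 0.08 SANDE points per 1% of the arm. An exit score would recover 0.03 to 0.06 of that, at a withdrawal rate that no document gives. The Schirmer endpoints lie outside the concern. What cannot be judged is the imputation model itself, because SAP 8.3.1 shows only one sentence. If that model uses the earlier post-baseline scores, the shift could be smaller still.

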### 3. Study Design and Procedures

#### 3.1 General Study Design

This will be a Phase 3, multicenter, vehicle-controlled, double-masked, randomized study conducted at approximately 20 sites in the United States. All subjects enrolled will have DED. The study will consist of Screening (Day -14) and Baseline (Day 1) visits as well as follow-up visits on Day 7, Day 14, Day 28, and Day 90 (Study Exit). There will also be a Day 60 dispensing visit. All subjects will be exposed to the Controlled Adverse Environment (CAE®) at the Screening visit.

At the end of the Screening visit, all qualified subjects will be assigned to administer AR-15512 vehicle BID (approximately 7:00h - 10:00h and 19:00h - 22:00h) to both eyes for approximately 14 days during the vehicle run-in period. After the vehicle run-in period, subjects will be re-evaluated at the Baseline (Day 1) visit for signs and symptoms of DED. Only subjects who requalify, based on inclusion/exclusion criteria, will be enrolled in the study and randomized in a 1:1 ratio within each site to receive 0.003% AR-15512 or AR-15512 vehicle to be administered BID (approximately 7:00h - 10:00h and 19:00h - 22:00h) as 1 drop in each eye for 90 days. Efficacy will be assessed at the Baseline (Day 1) visit and Days 7, 14, 28, and 90. At the end of the Day 90 visit, subjects will exit the study. Safety assessments will be conducted at each study visit. Study design is shown in Figure 1.

**Figure 1. Study Design**

Scheduled study visits in Table 1 (Screening, Baseline [Day 1], Day 7, 14, 28, 60, 90/Study Exit) will be referred as such in all tables and listings to enable reviewers to understand the assessment timing without referring to the protocol visit schedule. There is no Day 0, and Day 1 is the day of randomization, on which the subjects receive their first study intervention administration. For any event (or assessment) on or after Day 1, actual study day will be calculated as, (Date of Event) – (Date of First Dose of Study Intervention) +

1. For an event before Day 1, actual study day will be calculated as, (Date of Event) – (Date of First Dose of Study Intervention).

### **3.2 Schedule of Visits and Procedures**

The Schedule of Visits and Procedures is shown in Table 1.

**Table 1** Schedule of Visits and Procedures

According to the Clarification Letter #1, anesthetized Schirmer test is scheduled at both Screening and Baseline (Day 1) visit as stated in protocol

Section 7.2. The schedule of visits in the table doesn't have Baseline (Day 1) visit marked.

Visit 	Start of 2 Week Run-In (AR-15512 Vehicle)	Randomized Study Intervention Period (BID-OU, 1:1 Randomization 0.0033% AR-15512; AR-15512 Vehicle)							Early Termination
		Screening (Day -14)	Baseline (Day 1)	Day 7	Day 14	Day 28	Day 60	Day 90 (Study Exit)	
Visit Window (Days)	+3 	N/A	±2	±2	±2	±5	-2/+5		N/A
Informed consent	X								
Demographics	X								
Collection of used / unused study intervention	X			X	X	X	X	X	
Medical, ophthalmic, and surgical history	X			X	X	X	X	X	
Prior or concomitant medication review	X			X	X	X	X	X	
AE review	X			X	X	X	X	X	
Vital signs (heart rate and blood pressure)	X			X			X	X	
Urine pregnancy test (WOCBP only)	X			X			X	X	
Symptom questionnaire (VAS) (Ocular Discomfort, Eye Dryness)	X	X	X	X	X	X	X	X	
SANDE questionnaire (VAS)	X	X	X	X	X	X	X	X	
Corrected visual acuity									
Slit-lamp biomicroscopy	X	X	X	X	X	X	X	X	

		Randomized Study Intervention Period (BID-OU, 1:1 Randomization 0.003% AR-15512; AR-15512 Vehicle)															
Visit 	Start of 2 Week Run-In (AR-15512 Vehicle)	Screening (Day -14)		Baseline (Day 1)		Day 7		Day 14		Day 28		Day 60 		Day 90 (Study Exit)		Early Termination	
		X	X	X	X	X	X	X	X	X	X	X	X	X	X	X	
At least 10-minute rest period																	
CAE exposure			X														
Inclusion and exclusion criteria		X		X		X		X		X		X		X			
Randomization				X		X		X		X		X		X			
Dispensing of study intervention 				X		X		X		X		X		X			
At least 30 and up to 45-minute rest period					X		X		X		X		X		X		
Pre-drop unanesthetized Schirmer test						X		X		X		X		X			
At least 15 and up to 20-minute rest period							X		X		X		X		X		
In office administration of study intervention 								X		X		X		X			
Post-drop unanesthetized Schirmer test									X		X		X		X		
Hematology, chemistry, and urinalysis										X		X		X			
Intraocular pressure											X		X		X		
Dilated fundus exam												X		X			
Study exit													X		X		

 All office visits must be arranged at approximately the same time of day  $\pm$  1 hour.

 The Baseline visit should be scheduled between 11 and 14 days after the Screening visit. If absolutely necessary, the Baseline visit may be delayed up to 7 days (extending the run-in period to a maximum of 21 days).

 Administered every 5 minutes while in the CAE.

 Day 7 Randomized Intervention Kit is not to be dispensed home to the subject. A single vial is used at the Day 7 visit and then returned to the kit. The single used vial as well as remaining 4 unused vials are to be retained for accountability.

 Study intervention must be removed from the refrigerator at least 30 minutes before use.

 Dispensing and collection visit only.

